### **Maintaining Hydration:**

Sodium-glucose cotransporter type 2 inhibitors are associated with osmotic diuresis and volume depletion, which may lead to dizziness or hypotension, especially in the elderly. Before initiating study drug (at Screening, Run-in and Randomization) and during all on-site study visits thereafter, assess volume status in patients with renal impairment, the elderly, in patients with low SBP, or if receiving diuretics, angiotensin-converting-enzyme inhibitors, or angiotensin receptor blockers. All patients will be advised to maintain proper fluid intake and to consider increasing it if they sense greater thirst, more urine production, or if they feel dizzy or faint.

Patient communication cards will be printed with the following for patients with T2D:

“The following advice may be useful in helping you to maintain proper hydration and prevent dehydration:

- Dehydration is when your body loses too much fluid, frequently due to diarrhea or increased urination

- Consider increasing the amount of fluids you drink if:
  - You sense greater thirst than usual
  - You have a dry mouth or cracked lips
  - You have a fever
  - You have diarrhea or vomiting
  - You urinate more frequently or in larger amounts than usual
  - You get up in the middle of the night to urinate (more than usual)
  - You feel dizzy or light-headed
  - You exercise, or when it is hot outside

### **Recognizing Diabetic Ketoacidosis**

Potential GI adverse events occurring with sotagliflozin may mask presenting symptoms of diabetic ketoacidosis (DKA). Patient communication cards will be printed with the following:

If you have any of these symptoms on the list, then contact your study site immediately for assistance with managing your diabetes:

- Inability to maintain oral intake
- Generalized weakness
- Abdominal (belly) pain
- Increased weight loss
- Fever
- Frequent urination, including at night
- Fruity-scented breath
- Confusion
- Acute illness
- Consistently elevated blood glucose
- Feeling very thirsty or drinking a lot
- Nausea or vomiting
- Having trouble thinking clearly or feeling tired

It is possible to have DKA even if your blood glucose is not elevated. Regardless of your blood glucose level, if you have any of these symptoms on the list, then contact your study site regarding the need to be evaluated for possible DKA, which will include specific blood testing. If your study site is closed and your study doctor is not available, go to the nearest emergency room for evaluation.

If you are scheduled for a procedure or surgery that requires you to not take any food or liquids, please contact your study doctor for instructions on continuing study drug. In such cases your study doctor may advise you NOT to take your study drug from the day prior to the procedure or surgery until after the procedure or surgery is complete, and you are taking food and liquids as you normally do.”

Whenever AE data is collected or the patient reports DKA or intercurrent illness (including infections), generalized weakness, increased weight loss, GI symptoms including nausea, vomiting, or abdominal pain or other symptoms or signs that the Investigator believes may be consistent with DKA, then the site will determine if an assessment for DKA is appropriate. If laboratory testing confirms presence of metabolic acidosis, then the “Possible DKA” e-CRF will be completed.

## **Appendix C Measurement of blood pressure and pulse rate**

### **Equipment**

1. Blood pressure measurements will be taken by an automated BP monitor or a manual sphygmomanometer
2. Bladder Length – Should nearly or completely encircle the patient’s arm. For many adults, the standard “adult” size bladder is not long enough and the “large” size bladder is recommended
3. Bladder Width – Should be at least 40% of the bladder length

### **Patient Factors**

Extraneous variables associated with the measurement of BP should be minimized. These include:

1. Food intake, caffeine-containing beverages, cigarette smoking, or strenuous exercise within 2 hours prior to measurement
2. Full urinary bladder
3. The patient should not be allowed to talk while BP is being measured
4. The patient should be placed in the examination room and the cuff should be placed on the patient’s nondominant arm. The proper sized cuff should fit snugly with the lower edge 2 to 3 cm above the antecubital fossa.
5. The patient should be allowed to sit quietly in a comfortably warm place (temperature around 25°C or 77°F) for 5 minutes with the arm supported at heart level, preferably with the cuff in place and with no restrictive clothing on the arm. The patient should be encouraged not to tense his or her muscles.

### **Determination of the arm with the highest blood pressure**

At Visit 1 (Week -4), seated BP should be measured in both arms after 5-minute rest period, and then again after 1 minute in both arms in seated position. The arm with the highest SBP will be determined at this visit, and BP should be measured in this arm throughout the study.

### **Measurement Technique (24)**

At visit 1, immediately following arm selection, with the patient in the same position, an additional seated BP should be measured in the selected arm (at least 1 minute after last measurement).

[figure not shown]
At all other on-site visits, following the 5-minute rest period, 3 separate seated BPs should be measured in the arm selected at Visit 1, with at least 1 minute between BP measurements and with the cuff fully deflated between measurements.

All 3 BPs will be recorded in the patient's e-CRF. The mean of the 3 seated BPs will constitute the BP value for that visit.

Three seated pulse rate measurements will also be obtained. The mean of the 3 seated pulse rate measurements will constitute the pulse rate value for that visit.

## Appendix D General guidance for the follow-up of laboratory abnormalities by Sanofi

### NEUTROPENIA

[figure not shown]

#### Note:

- The procedures described in the above flowchart are to be discussed with the patient only in case the event occurs. If applicable (according to local regulations), an additional consent (e.g., for HIV testing) will only be obtained in the case the event actually occurs.
- For individuals of African descent, the relevant value of concern is <1000/mm^3

Neutropenia is to be recorded as an AE only if at least 1 of the criteria listed in the general guidelines for reporting AEs in [Section 10.4.2](#) is met.

[figure not shown]
### THROMBOCYTOPENIA

**Note:**

The procedures above flowchart are to be discussed with the patient only in case described in the the event occurs. If applicable (according to local regulations), an additional consent (e.g., for HIV testing) will only be obtained in the case the event actually occurs.

Thrombocytopenia is to be recorded as an AE only if at least 1 of the criteria listed in the general guidelines for reporting AEs in [Section 10.4.2](#) is met.

[figure not shown]

\*If unable to retest in 72 hours, use original lab results to decide on further reporting/monitoring/discontinuation.

Note:

- “Baseline” refers to ALT sampled at baseline visit; or if baseline value unavailable, to the latest ALT sampled before the baseline visit. The algorithm does not apply to the instances of increase in ALT during screening.
- See [Section 10.4](#) for guidance on safety reporting.
- Normalization is defined as ≤ULN or baseline value, if baseline value is >ULN.

[figure not shown]
### ACUTE RENAL FAILURE

Acute renal failure is to be recorded as an AE only if at least 1 of the criteria listed in the general guidelines for reporting AEs in [Section 10.4.2](#) is met.

### SUSPICION OF RHABDOMYOLYSIS

Suspicion of rhabdomyolysis is to be recorded as an AE only if at least 1 of the criteria in the general guidelines for reporting AEs in [Section 10.4.2](#) is met.

# EFC15166 Amended Protocol 01

APPENDIX D	SUMMARY OF STATISTICAL ANALYSES	91
APPENDIX E	STUDY FLOW CHART	94

LIST OF ABBREVIATIONS AND DEFINITION OF TERMS

ACR:	albumin: creatinine ratio
AESI:	adverse event of special interest
ALP:	alkaline phosphatase
ALT:	alanine aminotransferase
ANCOVA:	analysis of covariance
AST:	aspartate aminotransferase
ATC:	anatomic category
BMI:	body mass index
BP:	blood pressure
CEC:	Clinical Endpoint Committee
CI:	confidence interval
CKD:	chronic kidney disease
CRO:	contract research organization
CV:	cardiovascular
DBP:	diastolic blood pressure
DCCT:	Diabetes Control and Complications Trial
DILI:	drug-induced liver injury
ECG:	electrocardiogram
e-CRF:	electronic case report form
eGFR:	estimated glomerular filtration rate
EMA:	European Medicines Agency
EOSI:	event of special interest
EOT:	end of treatment
ESRD:	end stage renal disease
FPG:	fasting plasma glucose
GCR:	glucose: creatinine ratio
HbA1c:	hemoglobin A1c
HLGT:	high level group term
HLT:	high level term
HR:	heart rate
IFCC:	International Federation of Clinical Chemistry and Laboratory Medicine
IMP:	investigational medicinal product
IRT:	Interactive Response Technology
KM:	Kaplan-Meier
LDH:	lactic acid dehydrogenase
LLN:	lower limit of normal
LLT:	lower level term
MACE:	major adverse cardiovascular events
MAR:	missing at random
MDRD:	Modification of Diet in Renal Disease
MedDRA:	Medical Dictionary for Regulatory Activities
MI:	multiple imputation

Statistical Analysis Plan

Version: Final 3.0

Lexicon Pharmaceuticals Protocol No. EFC15166

Date of Issue: 21 November 2019

Covance Study ID: 000000155203

MNAR:	missing not at random
NIMP:	noninvestigational medicinal product
NTX:	N-terminal telopeptide
P1NP:	type 1 procollagen N-terminal
PCSA:	potentially clinically significant abnormality
PD:	pharmacodynamics
P-gp:	P-glycoprotein
PI:	Principal Investigator
PK:	pharmacokinetic
PRAC:	Pharmacovigilance Risk Assessment Committee
PT:	preferred term
PTH:	parathyroid hormone
SAE:	serious adverse event
SAP:	statistical analysis plan
SBP:	systolic blood pressure
SE:	standard error
SGLT:	sodium-glucose cotransporter
SGLT2:	sodium-glucose cotransporter type 2
SOC:	system organ class
T2D:	type 2 diabetes mellitus
TEAE:	treatment-emergent adverse event
UACR:	urine albumin: creatinine ratio
UGCR:	urine glucose: creatinine ratio
UGE:	urinary glucose excretion
ULN:	upper limit of normal
UTI:	urinary tract infection
WHO-DD:	World Health Organization-Drug Dictionary
β-CTX-1:	beta-C-terminal telopeptide

1 OVERVIEW AND INVESTIGATIONAL PLAN

1.1 STUDY DESIGN AND RANDOMIZATION

This is a Phase 3, multicenter and multinational, double-blind (single-blind Run-in Phase), placebo-controlled, parallel-group study. Patients were randomly assigned 1:1:1 to the following 3 treatment groups.

- Sotagliflozin 400 mg
- Sotagliflozin 200 mg
- Placebo

All patients will have a Screening Period comprised of an up to 2-week Screening Phase and a 2-week, single-blind placebo Run-in Phase prior to randomization. Following randomization, patients will have a 26-week, double-blind Treatment Period, 26-week, double-blind Extension Period, and a 4-week post-treatment Follow-up period (patients who prematurely discontinue the study treatment are expected to continue in the study).

At the end of the screening period, eligible patients will be centrally randomized (using permuted block randomization schedule) via an Interactive Response Technology (IRT).

The randomization will be stratified by:

- Hemoglobin A1c (HbA1c) at the screening ($\leq 8.5\%$ and $> 8.5\%$)
- Mean systolic blood pressure (SBP) at the screening visit (< 130 mmHg, ≥ 130 mmHg).

It is anticipated to randomize a total of approximately 276 patients.

1.2 OBJECTIVES

1.2.1 Primary objectives

The primary objective of this study is to demonstrate the superiority of sotagliflozin 400 mg versus placebo with respect to hemoglobin A1c (HbA1c) reduction at Week 26 in patients with type 2 diabetes (T2D) who have inadequate glycemic control and severe renal impairment.

1.2.2 Secondary objectives

- To assess the effects of sotagliflozin 200 mg versus placebo based on: Change from Baseline in HbA1c at Week 26
- To assess the effects of sotagliflozin 400 mg and 200 mg versus placebo, based on:
 - Change from Baseline in fasting plasma glucose (FPG) at Week 26

- Change from Baseline in body weight at Week 26
- Change from Baseline in systolic blood pressure (SBP) at Week 12 for patients with baseline SBP \geq 130 mmHg
- Change from Baseline in SBP at Week 12 for all patients
- Percentage change in urine albumin:creatinine ratio (UACR) from baseline to Week 26 (for patients with baseline UACR $>$ 30 mg/g)
- The proportion of patients with HbA1c $<$ 6.5%, $<$ 7.0% at Week 26
- To evaluate the safety of sotagliflozin 400 mg and 200 mg versus placebo over the 52 weeks of treatment.

1.2.3 Other objectives

[figure not shown]
To compare sotagliflozin 400 mg and 200 mg versus placebo with respect to:

- Change from Baseline in SBP at Weeks 26 and 52 for patients with Baseline SBP \geq 130 mmHg
- Change from Baseline in SBP at Weeks 26 and 52 for all patients
- Change from Baseline in HbA1c at Week 52
- Change from Baseline in FPG at Week 52
- Change from Baseline in body weight at Week 52
- Change from Baseline in estimated glomerular filtration rate (eGFR)
- Change from baseline on the following endpoints
 - Cystatin C
 - Urinary glucose excretion (UGE)
 - Urine glucose:creatinine ratio (UGCR)
 - Fructosamine
 - N-terminal prohormone of brain natriuretic peptide (NT-proBNP)
- Progression of kidney disease, based upon changes in eGFR or albuminuria
- Change from Baseline in additional measures of sitting blood pressure (BP)
- The proportion of patients requiring rescue for hyperglycemia during the 26-week double-blind treatment period
- To assess plasma levels of sotagliflozin and sotagliflozin-3-Oglucuronide in the sotagliflozin treatment arms

1.3 DETERMINATION OF SAMPLE SIZE

The sample size/power calculations were performed based on the primary endpoint. Assuming a common standard deviation of 1.2% and using a 2-sided test at a 0.05 α -level, 92 patients in each group will provide 80% power to detect a treatment difference of 0.5% in mean HbA1c change from Baseline to Week 26 between sotagliflozin 400 mg and placebo.

1.4 STUDY PLAN

The study flowchart can be found in [Appendix E](#).

1.5 MODIFICATIONS TO THE STATISTICAL SECTION OF THE PROTOCOL

This section summarizes major changes to the protocol statistical section with emphasis on changes after study start (after the first patient was enrolled).

The protocol history table below gives the timing, rationale, and key details of major changes to the protocol statistical section.

The first patient was enrolled on 12 September 2017. The study analysis will be conducted in 2 steps. The first step analysis is planned when all patients have been randomized and have their data at the minimum up to Week 26 collected and validated. The second step will be conducted at the end of the study.

Statistical Analysis Plan

Version: Final 3.0

Lexicon Pharmaceuticals Protocol No. EFC15166

Date of Issue: 21 November 2019

Covance Study ID: 000000155203

Table 1 - Protocol amendment statistical changes

Amendment Number	Date Approved	Rationale	Description of statistical changes
1	13-Dec-2017	Urgent coronary revascularization not adjudicated by CEC to be consistent with outcome trials	Urgent coronary revascularization not included in adjudication related analyses.
1	13-Dec-2017	5 half-lives of sotagliflozin prolonged to 15 days considering patients with severe renal dysfunction	5 half-lives of IMP updated from 5 days to 15 days; TEAE period updated accordingly
1	13-Dec-2017	Baseline eGFR defined as recommended by CDISC Therapeutic Area Data Standards User Guide for Diabetic Kidney Disease	For serum creatinine and eGFR, the baseline value is defined as the average of all values before the first dose of double-blind IMP for those randomized and exposed or before randomization for those who were randomized but never exposed to IMP.
1	13-Dec-2017	The effect in body weight is considered more closely associated with the planned indication.	Change in the order of secondary objectives, endpoints and multiplicity considerations

1.6 STATISTICAL MODIFICATIONS MADE IN THE STATISTICAL ANALYSIS PLAN

The statistical analysis plan history table below gives the timing, rationale, and key details for major changes to the statistical analysis features in the statistical analysis plan. Changes also incorporated in a protocol amendment are cross-referenced to [Table 1](#).

Statistical Analysis Plan

Version: Final 3.0
Lexicon Pharmaceuticals Protocol No. EFC15166

Date of Issue: 21 November 2019
Covance Study ID: 000000155203

[figure not shown]
[figure not shown]
Table 2 - Statistical analysis plan statistical changes

SAP version number	Date approved	Rationale	Description of statistical changes
1	04-Oct-2018	Urgent coronary revascularization not adjudicated by CEC to be consistent with outcome trials	Urgent coronary revascularization not included in adjudication related analyses*.
1	04-Oct-2018	5 half-lives of sotagliflozin prolonged to 15 days considering patients with severe renal dysfunction	5 half-lives of IMP updated from 5 days to 15 days; TEAE period updated accordingly*
1	04-Oct-2018	Baseline eGFR defined as recommended by CDISC Therapeutic Area Data Standards User Guide for Diabetic Kidney Disease	For serum creatinine and eGFR, the baseline value is defined as the average of all values before the first dose of double-blind IMP for those randomized and exposed or before randomization for those who were randomized but never exposed to IMP*.
1	04-Oct-2018	The effect in body weight is considered more closely associated with the planned indication.	Change in the order of secondary objectives and endpoints for the study
1	04-Oct-2018	Clarification on EOSI renal events	Details specified on renal events to be consistent with outcome studies in Section 2.1.4.2 .
1	04-Oct-2018	Clarification on ESRD	ESRD is defined in Section 2.4.4.3 consistent with CEC charter.
1	04-Oct-2018	[REDACTED]	[REDACTED]
1	04-Oct-2018	[REDACTED]	[REDACTED]
1	04-Oct-2018	Updating the wording to be consistency with CEC charter	"Unstable angina leading to hospitalization" changed to "Unstable angina requiring hospitalization"
2	05-Jun-2019	[REDACTED]	[REDACTED]
2	05-Jun-2019	Number of iterations for multiple imputation was changed	Number of iterations for multiple imputation was changed from 10000 to 2000
2	05-Jun-2019	Wording change to be consistent with CEC charter	"Heart failure leading to hospitalization" changed to "Heart failure requiring hospitalization"

Statistical Analysis Plan

Version: Final 3.0
Lexicon Pharmaceuticals Protocol No. EFC15166

Date of Issue: 21 November 2019
Covance Study ID: 000000155203

SAP version number	Date approved	Rationale	Description of statistical changes
2	05-Jun-2019	MedDRA version and dictionary updated	MedDRA version was updated to V22.0 and list of PTs for selected EOSI was updated
2	05-Jun-2019	Update categories of prior antidiabetic medication to cover all patients	Add "no antidiabetic therapy"
3	This version	Change in study Sponsor led to a strategic decision not to report the first step analysis in a standalone CSR	First step analyses will be combined with the second step analysis and both will be conducted at the end of the study in a single CSR The following sections/paragraphs are not applicable Section 2.4.4.4 – the last paragraph Section 3. – the first step analysis details Section 4. – the first data base lock
3	This version		
3	This version	Assess robustness of the ITT-based analyses	Identify possible need to conduct sensitivity analyses for PK anomalies
3	This version	Provide comparative analyses at Week 52 for the primary and secondary efficacy endpoints to further characterize the long-term effects of sotagliflozin	Apply statistical methods specified in Sections 1.6, 2.4.4.1, and 2.4.4.2 to the primary and secondary endpoints at Week 52
3	This version	Based on clinical guidelines for a higher A1C target for patients with chronic kidney disease.	Add another endpoint of proportion of patients with HbA1c <8%, at Week 26 and Week 52

* Change made in Protocol Amendment 1 dated 20-DEC-2017.

The first step analysis was conducted and reported for top line results; it was not used to inform a standalone Clinical Study Report (CSR) limited to just the 6-month data. A single CSR will be written for this study and will include the results coming from the analyses specified at both the first and second steps (see Section 3 of this SAP for more details).

The statistical methods detailed in this section will be performed in addition to those specified in other sections of the SAP. The majority of these additional assessments will serve as sensitivity analyses and will be used to support/qualify the robustness of results from the originally planned analyses.

The primary and continuous secondary efficacy endpoints for the overall population missing data at Week 26 (or Week 12 for SBP) visit will be imputed using a model built separately in each treatment group and estimated from the patients in the same treatment group who prematurely discontinue the IMP before the Week 26 (or Week 12 for SBP) visit but have the measurement for the endpoint (ie, retrieved dropouts). The imputation model will include the randomization strata and the corresponding baseline value. In cases of non-convergence during the imputations, the offending stratum will be identified and then will be dropped from the model. Considering that the number of retrieved dropout patients in each treatment group is expected to be small, a simple imputation model based on regression will be used with baseline measurement included as the predictor.

An alternative (back-up) imputation method will be used if the number of patients who prematurely discontinue the IMP before the Week 26 (or Week 12 for SBP) visit but have the measurement for the endpoint is < 5 in any treatment groups (ie, an insufficient number of retrieved dropouts to support the imputation method described above). This criterion will be assessed for each primary or continuous secondary efficacy endpoint.

In the back-up imputation method, missing post-baseline endpoint values at Week 26 (or Week 12 for SBP) will be imputed by the washout Multiple Imputation (MI) method under the missing not at random (MNAR) framework.

Missing endpoint data at the Week 26 (or Week 12 for SBP) in all treatment groups (sotagliflozin 400 mg, 200 mg and placebo) are imputed from a model estimated from patients in the placebo group who have the endpoint data available.

For patients in the sotagliflozin 400 mg and 200 mg group with missing data at Week 26 (or Week 12 for SBP), their missing values will be imputed using observed baseline and the observed primary endpoint data from placebo completers; no intermittent values from either placebo or the active treatment groups will be used.

For placebo patients, missing data will be imputed based on the placebo group data. Intermittent observed values will be used while imputing missing values at Week 26 (or Week 12 for SBP). In cases that a non-monotone missing data pattern occurs at the intermediate visits, these data points will be first imputed in the placebo group using the Markov Chain Monte Carlo (MCMC) option in PROC MI to achieve a monotone missing pattern for all placebo patients. The Week 26 (or Week 12 for SBP) endpoint values will be subsequently imputed from the multiple copies of the original dataset where each copy will have a monotone missing pattern.

The imputation models for the washout MI method will include the randomization strata and the corresponding baseline value. Missing data will be imputed using the regression method. In cases of non-convergence during the imputations, especially for the MCMC application in the placebo non-monotone datasets, graphical measures (eg, trace and autocorrelation plots) will be used to identify the offending variable and once detected, that variable(s) will be dropped from the model and the imputations will be re-run. These re-run models will use the same seed number and number of imputations as used in the original models.

For the overall population each of the completed datasets after the imputation will be analyzed using the Analysis of Covariance (ANCOVA) model with treatment groups (sotagliflozin 400 mg, 200 mg and placebo), randomization stratum of HbA1c ($\leq 8.5\%$, $> 8.5\%$), randomization stratum of SBP (< 130 mmHg, ≥ 130 mmHg), and country as fixed factors, and baseline HbA1c value as a covariate. Results from each analysis will be combined using Rubin's formula, to provide the adjusted mean change in HbA1c from Baseline to Week 26 (or Week 12 for SBP) for each treatment group, as well as the between-group difference (comparing sotagliflozin 400 mg versus placebo and sotagliflozin 200 mg versus placebo) and its associated 95% confidence interval (CI).

Patients in this study have undergone sampling for plasma levels of sotagliflozin and its main active metabolite in order to perform population PK analysis. Patients may be identified as those who have no detectable levels of active study drug or metabolite in their samples (ie, Below Limit of Quantification or BLOQ). When sample analysis has been completed and the study has been unblinded, explanations for some of these patients may be found: known non-compliance or sampling occurring after treatment had been discontinued. In other cases, drug intake history relative to the randomization assignment may not be fully explained. The ITT-based analyses specified in this document provides for a conservative assessment of the efficacy data should patients have been subjected to these unexplained non-compliance findings or PK 'anomalies'. To provide a broader perspective on the impact of these apparent errors in compliance, additional sensitivity analyses of the primary efficacy endpoint and continuous efficacy endpoints may be conducted. The need to perform such analyses, their specifics, and results will be provided in the Clinical Study Report (CSR), if applicable. The analysis methods applied to the patient subpopulations defined by the occurrence of the PK anomalies (eg, exclusion of patients with PK anomalies from the ITT dataset) will include the ANCOVA model using the retrieved dropout and/or washout MI methods, and the tipping point analyses previously specified in this section.

Analysis of the primary and secondary endpoints at Week 26 as specified in [Section 2.4.4.1](#) and [2.4.4.2](#) will be repeated for these same measures at Week 52, even though [Section 2.4.4.4](#) called for these analyses to be descriptive only. In addition, the sensitivity analysis methods described in this section will be applied to these variables at Week 52.

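### SAP Section 1.6 states two incompatible predictor sets for one retrieved-dropout imputation model, and the version with strata is unstable at the permitted minimum of 5 donors per arm

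*SAP*

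**What the plan says.** SAP Section 1.6 adds a retrieved-dropout imputation for the primary and continuous secondary endpoints at Week 26 (Week 12 for SBP). The same methods are to be applied at Week 52. The model is "a model built separately in each treatment group and estimated from the patients in the same treatment group", the donors being patients who stopped IMP early but still have the endpoint value.

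Three consecutive sentences then define the predictors:

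- The first adds the strata: "The imputation model will include the randomization strata and the corresponding baseline value".
- The second is a safeguard for a fit that fails: "In cases of non-convergence during the imputations, the offending stratum will be identified and then will be dropped from the model".
- The third says that, because the donors are expected to be few, "a simple imputation model based on regression will be used with baseline measurement included as the predictor".

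The paragraph after this sends an endpoint to the back-up method when the number of patients who stopped early "but have the measurement for the endpoint is < 5 in any treatment groups". Five donors in an arm therefore keep the retrieved-dropout model in use.

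Section 2.4.4.1 and the Appendix A Part 1 code use baseline alone in the retrieved-dropout step. There the strata appear only in the washout step. Appendix A has no separate code for the Section 1.6 analysis.

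**The concern.** The first and third sentences are both unconditional and name different predictors. The third cannot simply be read as replacing the first. If baseline were the only predictor, there would be no stratum in the model to drop, and the second sentence would have no purpose.

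The choice matters when donors are few, which the SAP itself expects. One version gives a usable but weak interval. The other can give an interval far wider than any plausible HbA1c effect. Section 1.6 says most of these additional analyses are there to support or qualify the robustness of the planned results, so the analysis should rest on one stated model.

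**Working it through.** **Inputs from the documents.** SAP Section 1.3: "Assuming a common standard deviation of 1.2% and using a 2-sided test at a 0.05" level, and "92 patients in each group will provide 80% power to detect a treatment difference of 0.5"% HbA1c. Section 1.1: "Patients were randomly assigned 1:1:1 to the following 3 treatment groups". Section 1.6: the two predictor sets, the threshold of 5 and Rubin pooling. Appendix A: 2000 imputations.

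**Design figure.** SE = 1.2 × √(2/92) = 0.177. Power = Φ(0.5/0.177 − 1.96) = 0.807 (0.803 with the t distribution), so 92 per arm reproduces. The complete-data 95% CI half-width is 1.96 × 0.177 = 0.35.

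**Residual degrees of freedom.** Strata plus baseline needs an intercept, two binary strata and baseline: 4 coefficients. Baseline only needs 2. With d donors, df is d − 4 or d − 2. Each imputation draws σ*² = RSS/χ²(df). Its mean is df/(df − 2) times the residual variance when df > 2, and is infinite at 1 or 2 df.

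| Donors per arm | Strata: df, mean inflation | Baseline only: df, mean inflation |
|---|---|---|
| 5 | 1, infinite | 3, 3.00 |
| 6 | 2, infinite | 4, 2.00 |
| 8 | 4, 2.00 | 6, 1.50 |
| 10 | 6, 1.50 | 8, 1.33 |
| 12 | 8, 1.33 | 10, 1.25 |

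If the strata were entered as one four-level factor, 5 donors would leave 0 df.

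**The non-convergence clause.** A monotone regression draw is closed-form. A full-rank fit with 1 df completes normally, so nothing triggers the clause.

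**Simulation.** Each trial used the regression draw above, 2000 imputations, ANCOVA on treatment, strata and baseline (country omitted) and Rubin pooling, with 250 trials per scenario. A stratum was dropped whenever the donor design was rank-deficient.

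The following inputs are assumptions and are not in the documents:

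- 5, 9 or 14 missing per arm (about 5, 10 or 15%);
- baseline HbA1c mean 8.3 and SD 1.0, with screening-to-baseline noise SD 0.4;
- 70% of patients with SBP of 130 mmHg or more;
- baseline slope −0.3 and residual SD 1.2;
- a 200 mg effect equal to 60% of the 400 mg effect;
- donors and missing patients distributed like the rest of their arm.

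Results for 400 mg versus placebo with 9 missing per arm:

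| Donors in every arm | Median half-width: baseline only | Median half-width: strata | Share significant: baseline only | Share significant: strata |
|---|---|---|---|---|
| 5 | 0.53 | about 18 (unstable) | 0.40 | 0.00 |
| 6 | 0.47 | 0.92 | 0.53 | 0.10 |
| 8 | 0.42 | 0.48 | 0.66 | 0.50 |
| 10 | 0.41 | 0.44 | 0.71 | 0.62 |
| 15 | 0.39 | 0.40 | 0.73 | 0.66 |

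A repeat run gave 0.42 versus 0.49 at 8 donors and 0.40 versus 0.42 at 12.

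- **Other missing counts.** With 5 and 14 missing, the half-widths at 5 donors are 0.45 versus about 15, and 0.66 versus about 29. At 6 donors they are 0.40 versus 0.67, and 0.56 versus 1.15.
- **Only the 400 mg arm has 5 donors, the others 15.** With 9 missing: 0.44 versus 5.2 (interquartile range for the strata version 0.93 to 16.5; 200 trials).
- **Number of imputations.** At 5 donors and 9 missing, the strata version gave 4.0, 7.6 and 18.8 with 100, 400 and 2000 imputations (120 replicates). The width grows with the imputation count, so no single figure at 5 donors is an estimate of anything.
- **Dropped strata.** With 5 donors in every arm, a stratum was dropped in at least one arm in about 60% of trials, and the result was still uninformative.

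**The case against.** The strongest reply is that the paragraph nearly resolves itself. Its last sentence gives few donors as the reason for the simple model, which is the situation where the strata version fails. All the retrieved-dropout code in Appendix A uses baseline only. The strata sentence looks like a leftover, since the washout model later in Section 1.6 has almost the same one. This makes baseline only the likelier intention. It does not explain why the paragraph also provides for dropping a stratum.

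The severe result is also a corner case, confined to about 5 or 6 donors. The documents give no donor count, and the protocol asks sites to keep patients in follow-up after they stop IMP, which should raise it. That limits the size of the point.

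Some table cells in Section 1.6 are blank, and the section refers to tipping-point analyses that are not visible in it. Further model detail may have been removed, but the sentences that can be read still conflict.

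A reader might infer more than the documents support:

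- **That the primary analysis is ambiguous.** It is not: its retrieved-dropout step is clearly baseline only.
- **That Section 1.6 contradicts Section 2.4.4.1 on the same method.** The methods differ. Section 2.4.4.1 uses retrieved dropouts only for patients who stopped IMP and washout for the rest. Section 1.6 applies the retrieved-dropout model to all missing endpoint values, in addition to the other planned analyses.
- **That a very wide interval would be reported as lack of robustness.** It could as easily be recognised as a failed imputation.
- **That this wording leaves a special opening for a choice made after seeing results.** The first-step results had been reported before SAP version 3, so that timing applies to all of its new text.

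**Conclusion.** The internal conflict in Section 1.6 is real: one model, two predictor sets, and no rule for choosing between them. At the permitted 5 donors the strata version has 1 residual degree of freedom and no usable interval. At 6 donors it roughly doubles the half-width. At 8 it adds about 0.06 to 0.07 HbA1c points, and by 12 the choice hardly matters. The degrees-of-freedom result needs no assumption beyond two binary strata entered as main effects. The half-widths rest on the assumed missing counts and distributions listed with the simulation.

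Severity is minor. Only the supportive Section 1.6 analyses at Week 26 (Week 12 for SBP) and Week 52 are affected, and no confirmatory test depends on them.

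**What to change.** In the retrieved-dropout paragraph of SAP Section 1.6, delete the sentence that puts the randomization strata in the model and the sentence on dropping a stratum. Baseline is then the only predictor. This fits the paragraph's own reasoning and the retrieved-dropout step in Section 2.4.4.1 and Appendix A Part 1. Keep the strata in the washout model later in Section 1.6.

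The cost is two deleted sentences, with no new data or analysis. With many donors, the loss from omitting the strata is negligible. The change does not make the analysis strong at 5 donors: with 9 missing per arm, baseline only still detects the design effect in only about 40% of simulated trials.
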